#### **11.3.2 Efficacy Analysis**

##### **11.3.2.1 Primary Efficacy Analysis**

The co-primary endpoints are the mean change from baseline in ADAS-Cog 11 at the end of the study (average of Weeks 40 and 48), and the mean change from baseline in the Alzheimer's Disease Cooperative Study – Activities of Daily Living (ADCS-ADL) at the end of the study (average of Weeks 40 and 48).

Each of the coprimary endpoints will be analyzed using a mixed-effects model for repeated measures (MMRM) with SAS PROC MIXED to compare change from baseline for COR388 HCl vs placebo. The MMRM model will include treatment group, study visit, site/country, treatment group by study visit interaction as fixed effects, and baseline MMSE (average of the last two non-missing assessments

collected prior to or at the day of first dose of the IP), ApoE4 status, and acetylcholinesterase inhibitor and/or memantine usage at baseline as factors with baseline score as a covariate using the ITT population. The analysis will be based on unstructured covariance matrix to model the within-subject errors. A Kenward-Roger approximation will be used for the denominator degrees of freedom.

Summary statistics (n, mean, standard deviation, minimum, median, and maximum) will be presented for the observed values for each of the coprimary endpoints at each time point for the ITT population, including weeks 40 and 48 separate as well as averaged. Summary statistics will also be presented for the change from baseline values to each postbaseline time point as listed above.

The Type I error for the interim and final analysis will be adjusted using the Lan-DeMets spending function. Detailed of the adjustment is presented in [Section 11.3.2.3](#) and in the [SAP](#).

Treatment comparisons of 40 mg and 80 mg COR388 HCl to placebo will be adjusted using Benjamini-Hochberg multiplicity adjustment procedure ([Benjamini and Hochberg, 1995](#) and [Benjamini and Yekutieli, 2001](#)). Both treatment comparisons, 40 mg (low dose) and 80 mg COR388 HCl (high dose) to placebo are considered of equal interest.

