**Efficacy Evaluations**

The two co-primary endpoints are:

- Mean change in Alzheimer's Disease Assessment Scale-Cognitive Subscale 11 (ADAS-Cog 11) from baseline to the end of treatment period.
- Mean change in Alzheimer's Disease Cooperative Study Group-Activities of Daily Living (ADCS-ADL) from baseline to the end of treatment period.

Secondary endpoints in all subjects include:

- Change in Clinical Dementia Rating-Sum of Boxes (CDR-SB).
- Change in Mini-Mental State Examination (MMSE)
- Change in Neuropsychiatric Inventory (NPI)

Exploratory endpoints in all participating subjects include change from screening/baseline and/or Visit 2 to the end of treatment period in the following measures:

- 
- Blood-based biomarkers in serum and peripheral blood mononuclear cells (PBMCs); and
- Saliva biomarkers of *P. gingivalis* infection and inflammation.
- Cerebrospinal fluid:
  - CSF A $\beta$ 42, total Tau, and phosphorylated Tau;
  - Bacterial DNA in the CSF based on quantitative polymerase chain reaction (qPCR) and sequencing; and
  - CSF biomarkers.

Exploratory endpoints in subjects participating in sub-studies include change from screening/baseline to the end of treatment period in the following measures:

- Winterlight Speech Assessment (only in English speaking (primary language) subjects and only in the US and UK);
- Magnetic resonance imaging sub-study (subjects who have MRIs done in conjunction with the study):
  - Hippocampal volume; and
  - Cortical thickness.

- Clinical periodontitis sub-study (subjects enrolled at selected sites):
  - Pocket Depth (PD);
  - Clinical Attachment Level (CAL) at 6 sites per tooth (distobuccal [DB], buccal [B], mesiobuccal [MB], distolingual [DL], lingual [L], and mesiolingual [ML]);
  - The percentage of sites with Bleeding on Probing (BOP); and
  - Biomarkers of *P. gingivalis* infection and inflammation in subgingival plaque (SGP) and buccal cell swabs.

**Safety Endpoints** Safety endpoints include:

- The incidence and severity of TEAEs;
- Vital signs and physical examinations;
- Laboratory values;
- MRI scans;
- 12-lead ECGs; and
- C-SSRS.

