**Statistical Considerations**

The study is designed as an adaptive trial and will allow for stopping early for efficacy, futility and potential adjustment in sample size based on the results of a planned interim analysis. Approximately 573 subjects are planned to be randomized 1:1:1 per treatment group (191 per treatment group) assuming approximately 10% will drop out prior to 48 weeks. This sample size would provide approximately 90% power to detect a 2.5-point difference between active treatment group and placebo with respect to change from baseline ADAS-Cog 11 score at Week 48, assuming a standard deviation of 7.1 at a two-sided significance level of 0.05 using a two-sided test. The ADCS-ADL was added as a co-primary outcome, with assumptions of a 3.9-point difference between the active treatment group compared to placebo with respect to change from baseline on ADCS-ADL, assuming a standard deviation of 10.5, providing approximately 95% power on this outcome measure, with approximately 90% power for the overall co-primary outcomes, depending on their correlation.

An unblinded interim analysis will be conducted by a firewalled independent statistician (all clinical trial personnel will remain blinded) when approximately 100 subjects per arm have completed the Week 24 visit. Overwhelming efficacy, futility and sample size adjustment will be evaluated. The Lan-DeMets spending function will be used to determine the test boundaries. If the interim analysis is conducted when approximately 300 subjects have completed the Week 24 visit, then a significance level of 0.005 will be used for the interim analysis and a

significance level of approximately 0.0456 will be used for the final analysis.  
Further details are provided in the statistical analysis plan (SAP).

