#### **4.1.2 Efficacy Evaluations**

##### Primary Endpoint

The two co-primary endpoints are:

- Mean change in Alzheimer's Disease Assessment Scale-Cognitive Subscale 11 (ADAS-Cog 11) from baseline to the end of treatment period; and
- Mean change in Alzheimer's Disease Cooperative Study Group-Activities of Daily Living (ADCS-ADL) from baseline to the end of treatment period.

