### **11.2 Determination of Sample Size**

The study will have an adaptive design that allows for potential adjustment in sample size and evaluation of efficacy based on the results of a planned interim analysis. An unblinded interim analysis will be conducted by a firewalled independent statistician (all clinical trial personnel will remain blinded) when approximately 100 subjects per arm have completed the Week 24 visit. Approximately 573 subjects are planned to be randomized 1:1:1 per treatment group (191 per treatment group) assuming approximately 10% will drop out prior to 48 weeks. Due to the planned interim analysis, adjustments will be made to the alpha level used in the final analysis to control for overall Type I error. The final criterion for efficacy to be used at the interim and final analysis depends on when the interim analysis occurs. The Lan-DeMets method modified according to [Chen et al. \(2004\)](#) to account for correlation between endpoints used at the interim and final analyses will be used to calculate the level of significance for each analysis. As originally planned, with 573 subjects randomized, an expected 10% discontinuation rate, and a single primary outcome, a total of 172 subjects per treatment group would provide approximately 90% power to detect a 2.5-point difference between the active treatment group compared to placebo with respect to change from baseline on the ADAS-Cog 11, assuming a standard deviation of 7.1, respectively at a significance level (alpha) of 0.05 using a two-sided test. The ADCS-ADL was added as a co-primary outcome, with assumptions of a 3.9-point difference between the active treatment group compared to placebo with respect to change from baseline on ADCS-ADL, assuming a standard deviation of 10.5, providing approximately 95% power on this outcome

measure, with approximately 90% power for the overall co-primary outcomes, depending on their correlation.

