#### **11.3.2.1.1 Sensitivity Analyses**

The following sensitivity analyses will be performed on each of the co-primary endpoints:

- Repeat above analysis using the PP population.
- Impute missing values using a last z-score carried forward method (converted back to the original scale) and analyze the primary endpoint (Average of Weeks 40 and 48 only) using analysis of covariance (ANCOVA) with fixed effects of treatment group, ApoE4 status, acetylcholinesterase inhibitor and/or memantine usage, site/country and baseline MMSE with baseline score as a covariate.
- Pattern mixture model:  
The pattern-mixture model approach uses a control-based pattern imputation ([Ratitch and O'Kelly, 2011](#)). With this approach, subjects who discontinued from the COR388 HCl 80 mg or COR388 HCl 40mg treatment group will be assumed to follow a similar outcome trajectory as subjects from the placebo (control) arm and subjects who discontinued from placebo (control) treatment are modeled as completers within their own arm (MAR within control arm). That is, the imputation model for the missing observations in the active treatment groups are constructed not from the observed data in the corresponding active treatment group but rather from the observed data in the placebo treatment group. This model is also the imputation model that will be used to impute missing observations in the placebo treatment group. This will

be implemented by utilizing the MONOTONE REG statement of SAS® PROC MI with the option nimpute=5.

Pattern mixture model tends to overestimate the already very large variability in Alzheimer's disease data, these model results are likely to be much less able to discriminate treatment differences than the primary model. The results of this imputation method will primarily be used to assess the potential bias of the main model estimates due to dropout by comparing the estimates between the primary and sensitivity models.

Additional subgroups including gender, demographic, and other baseline characteristics may be performed. Further details will be given in the SAP.

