### **11.3.2.3 Multiplicity**

To control for type I error, for the interim and final analysis will be adjusted using the Lan-DeMets spending function. If the study does not stop at the interim analysis (i.e., 24 weeks ADAS-Cog and CDR-SB as co-primary endpoints) for overwhelming efficacy or futility, the study will retain its original design and the final analysis will be based on 48 weeks of treatment with ADAS-Cog and ADCS-ADL as co-primary endpoints. Because of the changes in co-primary endpoint at 48 weeks (i.e., CDR-SB 24-week replaced by ADCS-ADL at 48-week and ADAS-Cog 24-week replaced by ADAS-Cog 48-week), the Lan-DeMets correction for sequential analysis will be further adjusted as described in [Chen et al., \(2014\)](#). This adjustment will account for the correlation between the outcomes and time points. The boundaries will be calculated to account for the change in timing of evaluation and endpoint and the more conservative boundary will be used for final analysis at 48-week.

At both the interim analysis at 24 weeks and final analysis at 48 weeks, to adjust for comparison between placebo and each of the two doses, Benjamini-Hochberg multiplicity adjustment procedure ([Benjamini and Hochberg, 1995](#) and [Benjamini and Yekutieli, 2001](#)) will be used. Both treatment comparisons, 40 mg (low dose) and 80 mg COR388 HCl (high dose) to placebo are considered of equal interest.

Treatment comparisons of 40 mg and 80 mg COR388 HCl to placebo for the secondary endpoints at 24-week or 48-week will be performed only if both co-

primary endpoints compared to placebo are statistically significant at the level of approximately 0.005 or 0.0456 for the interim analysis and final analysis, respectively. Otherwise, secondary endpoints will be presented using descriptive statistics.

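### Is the 90% power for ADAS-Cog 11 stated for Week 48 when the primary test uses the average of Weeks 40 and 48?

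*Protocol*

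**What the plan says.** The endpoint is defined in Section 11.3.2.1: "The co-primary endpoints are the mean change from baseline in ADAS-Cog 11 at the end of the study (average of Weeks 40 and 48"; the ADCS-ADL endpoint carries the same averaging. Section 11.3.2.1.1 repeats it when describing the ANCOVA sensitivity analysis ("analyze the primary endpoint (Average of Weeks 40 and 48 only"). The descriptive summaries are to show the two visits "including weeks 40 and 48 separate as well as averaged".

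Power appears twice. In the synopsis, under Statistical Considerations, about 90% power for a 2.5-point difference is given with "respect to change from baseline ADAS-Cog 11 score at Week 48". Section 11.2 gives the same inputs "with respect to change from baseline on the ADAS-Cog 11, assuming a standard deviation of 7.1" and names no week. The ADCS-ADL inputs (3.9 points, SD 10.5) have no week in either place.

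Elsewhere the wording is more general. The endpoint lists in the synopsis and in Section 4.1.2 speak of change "from baseline to the end of treatment period". Section 11.3.2.3 describes the move from interim to final endpoints as "CDR-SB 24-week replaced by ADCS-ADL at 48-week and ADAS-Cog 24-week replaced by ADAS-Cog 48-week".

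**The concern.** A power statement should describe the statistic that will be tested. Here the only one that names a time point names Week 48, while the test is on the mean of two visits. The protocol itself treats these as different quantities, since it summarises the visits both separately and averaged.

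The two need not have the same power. Averaging two correlated measurements lowers the SD, which raises power. If the treatment effect is still growing between Week 40 and Week 48, averaging also shrinks the difference, which lowers power. If the second effect dominated, 573 subjects might give less than the claimed 90% for the planned test. The labels in Section 11.3.2.3 add to the impression that the final endpoint is named in more than one way.

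**Working it through.** **Inputs from the protocol.** 191 randomised per group and about 10% dropout: 191 × 0.9 = 171.9, i.e. 172 per group. ADAS-Cog 11 difference 2.5, SD 7.1, two-sided alpha 0.05 (Section 11.2 and synopsis).

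**The stated figure.** The standard error of the difference is 7.1 × √(2/172) = 0.766, and 2.5/0.766 = 3.27. Power is Φ(3.27 − 1.96) = 0.904. The noncentral t gives 0.902, and the final-analysis alpha of 0.0456 gives 0.897. For 90% power at 0.05, 170 per group are needed. The claim of about 90% is therefore right for a 2.5-point difference with SD 7.1, whatever time point those inputs describe.

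**Reading 1: 2.5 and 7.1 describe the average.** Power for the primary test is then the same 0.904.

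**Reading 2: 2.5 and 7.1 describe Week 48.** Let f be the Week 40 effect as a fraction of the Week 48 effect, s the Week 40 SD as a fraction of the Week 48 SD, and r the correlation between the two changes. Then:

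- difference in the average = 2.5 × (1 + f)/2
- SD of the average = 7.1 × √(1 + s² + 2rs)/2

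The protocol gives none of f, s or r. The values below are assumptions, with r from 0.6 to 0.9 and 172 per group:

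| Effect at Week 40 | s | Difference | SD of average | Power (r = 0.6 to 0.9) |
|---|---|---|---|---|
| same as Week 48 | 1 | 2.50 | 6.35 to 6.92 | 0.955 to 0.918 |
| same as Week 48 | 0.92 | 2.50 | 6.10 to 6.64 | 0.967 to 0.937 |
| 40/48 of Week 48 | 1 | 2.29 | 6.35 to 6.92 | 0.917 to 0.867 |
| 40/48 of Week 48 | 0.92 | 2.29 | 6.10 to 6.64 | 0.936 to 0.892 |
| 40/48 of Week 48 | 40/48 | 2.29 | 5.83 to 6.34 | 0.954 to 0.918 |
| 70% of Week 48 | 1 | 2.125 | 6.35 to 6.92 | 0.874 to 0.813 |
| 70% of Week 48 | 0.92 | 2.125 | 6.10 to 6.64 | 0.898 to 0.843 |

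For an effect proportional to time with equal SDs, the average has the same power as Week 48 when (44/48)² = (1 + r)/2, i.e. r = 0.68. Power for the average is higher below that correlation and lower above it. When effect and SD both scale with time (fifth row), power falls to 0.904 only at r = 1.

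The table is a range of plausible cases, not a bound. It shows that the sign of any difference cannot be settled from the document.

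**The other wordings side by side.** The design rationale in Section 4.1.1 places the 2.5-point target at the end of the treatment period, and the endpoint lists use the same general term. Section 11.3.2.1 then makes the end of the study specific as the Week 40/48 average. In Section 11.3.2.3, the 24-week and 48-week labels separate the interim look from the final one. These passages are less detailed than Section 11.3.2.1 and do not contradict it. Only the synopsis phrase is out of line.

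**The case for a change.** The best case for a change has three parts. First, the sentence in the synopsis is current text, and an SAP that gives more detail would not correct it. Second, the power claim justifies 573 subjects, and a sample size re-estimation is planned on top of it. Third, Section 11.3.2.3 adjusts the final boundary for the correlation between outcomes and time points. The correlation of a Week 24 measure with Week 48 need not equal its correlation with the Week 40/48 average, so the final endpoint entering that calculation matters. If the effect at Week 40 is well short of the Week 48 effect, power for the average could be in the low 80s.

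The first part stands as a matter of wording. The second does not go far: the low figures rest wholly on assumed Week 40 inputs, and equally reasonable inputs give more than 90%. The planning figure is also a simple two-group comparison, whereas the planned test is a covariate-adjusted MMRM, so it was never an exact statement of power for that test. On the third, Sections 11.3.2.1 and 11.3.2.1.1 both define the final endpoint as the average. An analyst computing the boundary would take the correlation from that definition, and Section 11.3.2.3 already commits to the more conservative boundary.

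**Conclusion.** No change to the plan is needed. The synopsis gives a time point for the ADAS-Cog 11 planning inputs that differs from the tested endpoint, and Section 11.2 and the ADCS-ADL inputs name none. This is loose wording around a planning figure. The 90% reproduces at 0.904 from its own inputs. If those inputs describe the average, it applies directly to the primary test. If they describe Week 48, power for the average lies somewhere between about 0.81 and 0.97 under the assumed Week 40 effects (70% to 100% of Week 48), SD ratios (40/48 to 1) and correlations (0.6 to 0.9). Nothing in the protocol narrows that range or shows it to be unfavourable.

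The endpoint, the model and the visits are fixed in Section 11.3.2.1, and following them as written gives a sound analysis. Naming the time point of the planning inputs would make the synopsis tidier without changing the analysis, any decision or the interpretation of the result.

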### **5.2 Randomization to Treatment Groups**

Subjects who meet all eligibility criteria will enter the treatment period and will be randomized 1:1:1 to receive 40 mg COR388 HCl, 80 mg COR388 HCl, or placebo twice a day. Randomization will be stratified by baseline MMSE (MMSE  $\geq 12$  and  $\leq 18$ , and MMSE  $\geq 19$  and  $\leq 24$ ) and Apolipoprotein E (ApoE4 positive either homozygous or heterozygous vs. all others) genotype to assure balanced distribution of mild and moderate AD and a balanced distribution of ApoE4 subjects, across treatment arms. All participants will be centrally assigned to randomized

study intervention using an Interactive Response System (IRS). All subjects in the open label extension portion of the study will receive 40 mg or 80 mg COR388 HCl.

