### **6.1 Inclusion Criteria**

Subjects will be eligible to participate in this study if they meet all of the following criteria:

1. Subject has provided full written informed consent prior to the performance of any protocol-specified procedure; or if unable to provide informed consent due to cognitive status, subject has provided assent and a legally authorized representative has provided full written informed consent on behalf of the subject.
2. Caregiver has provided full written informed consent, on a separate informed consent form (ICF), on his/her own behalf prior to the performance of any protocol-specified procedure.

3. Male and female subjects must be 55 years to 80 years of age, at the time of consent.
4. Subject has probable AD dementia according to the NIA-AA criteria ([McKhann 2011](#)) with clinical evidence of progressive cognitive decline in the last year. Clinical decline will be determined based on serial cognitive test scores, if available, or subject/caregiver report as documented by the Investigator.
5. Subject has an MMSE score between 12 and 24 inclusive at both screening and Visit 2 and a  $\leq 3$ -point difference between these visits.
6. Subject has a Modified Hachinski score  $\leq 4$  at screening.
7. Subject has brain MRI scan consistent with the diagnosis of AD performed during the screening period. Computed Tomography scan can be used only if the subject has an absolute contraindication for MRI.
8. Subject has a primary caregiver willing to accept responsibility for supervising the treatment (e.g., administering study drug), accompanying the study subject to clinic visits and assessing the condition of the subject throughout the study in accordance with all protocol requirements.
9. Subject is not likely to experience a change in living conditions (e.g., institutionalization, moving to a different city, etc.), or change in primary caregiver, during participation in the trial.
10. Subjects with background symptomatic therapy with acetylcholinesterase inhibitors, and/or memantine, are allowed as long as the dose has been stable for 90 days prior to screening and no changes are planned during the study.
11. Subjects who have occasional use of sedative agents are acceptable, but these agents should not be given within 48 hours prior to cognitive assessments.

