## 8.3 Mini-Mental State Examination (MMSE)

The Mini-Mental State Examination (MMSE) ([Folstein 1975](#)) is a widely used and validated assessment to be used to evaluate inclusion eligibility as well as an exploratory measure. The MMSE will be administered by a trained rater to assess the level of cognitive impairment. MMSE will be assessed as early in the screening period as possible. Subjects with MMSE score of 12-24, inclusive, will have the rest of their screening procedures performed or scheduled. The MMSE will be administered at Screening (Visit 1), Visit 2, Visit 5, Visit 7, Visit 9, Visit 10 (or Early Termination), and Visit 11 (Safety Follow-up Visit). The MMSE score should be  $\geq 12$  and  $\leq 24$  at both Screening (Visit 1) and Visit 2, and a  $\leq 3$ -point difference between these visits, for inclusion in the study. The MMSE takes approximately 20 minutes to complete.

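### The primary model enters an averaged MMSE as a factor with no levels given, and does not name the MMSE stratum used to randomise

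*Protocol*

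**What the plan says.** Protocol section 5.2: "Randomization will be stratified by baseline MMSE" in two bands, 12 to 18 and 19 to 24, and by ApoE4 carrier status. The synopsis and section 8.4 repeat this. None of the three says whether the score is the screening value, the Visit 2 value or a combination.

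Section 6.1, criterion 5: "Subject has an MMSE score between 12 and 24 inclusive at both screening and Visit 2", with the two scores no more than 3 points apart. Section 8.3 sets the schedule: "The MMSE will be administered at Screening (Visit 1), Visit 2, Visit 5, Visit 7, Visit 9" and later visits. Two scores are therefore scheduled before the first dose.

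Section 11.3.2.1 defines the MMSE term of the primary MMRM as "baseline MMSE (average of the last two non-missing assessments" up to the day of first dose. The list of terms ends with "memantine usage at baseline as factors with baseline score as a covariate". The averaged MMSE thus stands with ApoE4 status and background AD drug use as a factor, and only the endpoint's own baseline is called a covariate. No levels or cut-points are given. The sensitivity ANCOVA in section 11.3.2.1.1 likewise puts MMSE with the fixed effects: "site/country and baseline MMSE with baseline score as a covariate".

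**The concern.** An analysis that follows stratified randomisation normally adjusts for the factors used to stratify. ApoE4 status is in the model. The MMSE stratum is not named, and a related variable in an awkward form takes its place. A mean of two whole-number scores moves in half points, so treating it as categorical leads either to many small classes or to an unstated grouping.

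At stake are a little precision on both co-primary endpoints and a single agreed reading of the confirmatory model. As written, analysts could fit a factor with many levels, a two-level factor with a hole in it, or a linear term, all under the same sentence.

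**Working it through.** **The plan's own figure.** Section 11.2 says "a total of 172 subjects per treatment group would provide approximately 90% power to detect a 2.5-point difference", with SD 7.1 and two-sided alpha 0.05. Power = Φ(δ / (SD·√(2/n)) − 1.96) = Φ(2.5 / (7.1·√(2/172)) − 1.96) = Φ(3.265 − 1.96) = 0.904. The stated 90% is reproduced. The calculation has no MMSE term.

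**Possible values of the average.** Inputs are whole-number scores of 12-24 at both visits, at most 3 points apart (section 6.1). Counting all combinations gives 79 admissible (screening, Visit 2) pairs and 25 distinct averages: 12 to 24 in steps of 0.5.

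**Reading 1: class factor by value (the literal one).**
- It costs up to 25 − 1 = 24 df. Stratum plus a linear MMSE term costs 2.
- With 172 × 3 = 516 evaluable subjects, a rough variance ratio is (516 − 2)/(516 − 24) = 1.045, and √1.045 = 1.022. The standard error is about 2% larger.
- Simulation with an assumed MMSE distribution and assumed slopes on MMSE gave 2-3%, in agreement.
- Everyone has a level and nobody is dropped.
- If Visit 2 alone set the stratum, averages of 17.5, 18, 18.5, 19 and 19.5 each mix subjects from both strata, so the factor does not fully recover it.

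**Reading 2: two levels cut at the randomisation limits.**
- Four pairs average 18.5 and fit neither band: (17,20), (18,19), (19,18), (20,17).
- If the Visit 2 score set the stratum, four more pairs change band: (16,19), (17,19), (20,18), (21,18).
- If the screening score did, the four are (18,20), (18,21), (19,16), (19,17).
- If the average did, none change, but 18.5 still has no band.

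The documents give no MMSE distribution, so the shares below rest on assumed ones, with both entry rules applied and measurement SD from 1 to 2:

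| Assumed true MMSE | Average exactly 18.5 | Changes band (stratified on Visit 2) |
|---|---|---|
| Normal, mean 18.5, SD 3.5 | 6.3-6.6% | 3.5-5.7% |
| Normal, mean 20, SD 3 | 6.5-6.8% | 3.6-6.0% |
| Uniform, 10 to 26 | 4.3-4.8% | 2.4-4.3% |

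Of 573 randomised, that is about 24-39 subjects at 18.5 and 13-34 in a different band. The second column excludes the 18.5 subjects, so the two do not overlap.

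**Reading 3: continuous term.** There is no gap and no change of level, but it contradicts the word factors and still omits the stratum.

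**The case against.** The strongest reply is that no harm to validity is shown, and that stands. The average is measured before dosing, so adjusting for it does not bias the treatment comparison. Averaging reduces measurement noise, and a fine-grained severity measure can explain more variance than a two-level stratum.

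Three stronger readings are tempting, and the documents do not support them.

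- *That subjects averaging 18.5 will be lost.* The protocol never cuts the average at 18/19. Loss needs that unstated cut and then a decision to code 18.5 as missing. If both happened and about 6.5% were dropped, 172 per arm would become about 161 and power Φ(2.5/(7.1·√(2/161)) − 1.96) = 0.885. That is under 2 points, and hypothetical.
- *That the model cannot adjust for the stratum on any reading.* If the average itself set the stratum, a by-value factor contains the stratum completely. Section 7.2 places the Visit 2 MMSE before randomisation, so the average was available. Against this, section 7.2 and footnote 6 of Table 1 use the term baseline MMSE for the score verified before the lumbar puncture, which suggests the single Visit 2 value. The protocol does not settle it.
- *That 8-9% change stratum on top of 6-7% unclassified.* The 8-9% arises only when the 18.5 subjects are placed in one band. Reporting both counts some subjects twice.

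It can also be said that coding of covariates belongs in the SAP, which is not available here. That would answer a silence. Section 11.3.2.1 is not silent: it defines the term as an average, lists it as a factor and separates it from the covariate.

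**Conclusion.** The point holds as a poorly specified primary model with incomplete adjustment for a stratification factor. Firm from the text alone: the MMSE stratum is not named, the averaged MMSE is listed as a factor without levels, it can take up to 25 values, and four admissible score pairs average 18.5.

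The sizes are small. The literal reading costs up to 24 df and about 2-3% in standard error, given an assumed MMSE distribution. The 6-7% at 18.5 applies only if the average is cut at the randomisation limits. The further 3.5-6% also needs randomisation to have used a single visit's score. Both shares are lower under a flat MMSE distribution. There is no bias, no error in alpha, and no change to the stated power unless subjects are dropped. It is worth correcting because the confirmatory model should have one reading and the correction is nearly free.

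**What to change.** In section 11.3.2.1 (MMRM) and section 11.3.2.1.1 (ANCOVA), replace the averaged MMSE factor with the two-level MMSE stratum as recorded in the Interactive Response System, alongside ApoE4 status. If the averaged MMSE is wanted for precision, add it as a continuous covariate, not as a factor. In sections 5.2 and 8.4, state which MMSE score defines the stratum.

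The cost is a few words in each place and the same change in the SAP. No new data are needed. The stratum uses 1 df and a linear average 1 more, every subject has a level, and the planned sample size is unchanged.
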